5.7 General Concomitant Medication and Supportive Care Guidelines

No restrictions to medications exist with regards to the ablation procedures. However, clopidogrel (anti-platelet medication) should be discontinued for 5-7 days pre-procedure, unless the risk of discontinuation outweighs the risk of bleeding. Blood thinners such as warfarin should be discontinued for 5-7 days prior to the procedure as well.

5.8 Women of Childbearing Potential

Women of childbearing potential (women with regular menses, women with amenorrhea, women with irregular cycles, women using a contraceptive method that precludes

withdrawal bleeding, and women who have had a tubal ligation) are required to have a negative pregnancy test (serum or urine) within 1 day prior to the ablation procedure.

5.9 Duration of Therapy

Tumor ablation is a one-time procedure. If at any time prior to or during ablation, the constraints of this protocol are considered to be detrimental to the patient's health and/or the patient no longer wishes to proceed with ablation, this treatment should be discontinued and the reason(s) for discontinuation documented in the case report forms.

Because the ablation procedures are intended to replace maintenance chemotherapy, chemotherapy should not resume following ablation therapy. If the treating physician feels it is warranted (i.e., the patient develops a lesion that is not amenable to ablation), then the patient will be considered to have progressed and will be taken off trial and replaced.

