2.0 OBJECTIVES

2.1 Primary Objectives

To determine the progression-free rate at 3 months in patients with metastatic sarcoma stable on chemotherapy whose lesions have undergone ablation. PFR is defined as the percentage of patients with no progression (local recurrence of an ablated lesion or the appearance of a new lesion) at 3 months after ablation.

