5.6 Evaluability

All patients who undergo ablation are evaluable for toxicity. Patients are evaluated from date of first procedure and for 30 days thereafter.

All patients who undergo ablation are evaluable for disease response provided they have had at least one disease assessment.

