5.10 Duration of Follow-up

Patients will be followed every 9 weeks for the first year, every 12 weeks for the second year, and then every 6 months for 5 years or until death, progression, consent is withdrawn, or the study is closed, whichever occurs first. Patients will be followed by CT or PET scan and office visits every 9 weeks. CT and PET scans can be performed at outside facilities and mailed to us for review by our radiologists. Patients removed from study for unacceptable adverse events will be followed until resolution or stabilization of the adverse event. After progression, patients will be followed for survival every 3 months.

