9.4.5 Other Definitions

Progression-free rate: PFR is defined as the percentage of patients with no progression (local recurrence of an ablated lesion or the appearance of a new lesion) at 3 months after ablation.

Overall survival: OS is defined as the time from diagnosis of metastatic disease to the time of death.

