11.0 STATISTICAL CONSIDERATIONS

11.1 Power

Our power analysis is based on the following hypotheses. The null hypothesis assumes that the 3-month progression-free survival (PFS) for treatment with ablation therapy is

overall 20% for patients with metastatic sarcoma. We hypothesize in the alternative hypothesis that the 3-month PFS will be at least 40% with ablation therapy. This is based on data from a clinical trials database used to provide reference values for conducting phase II studies in sarcoma with PFR as the principal endpoint (5). An enrollment of 36 patients can achieve at least 80% power to conclude that the alternative hypothesis is true based on a two-sided test of one-sample proportion at a significance level of 0.05.

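### Section 5.9 replaces patients because they have progressed, and no section says they stay in the 3-month PFR; if their places among the 36 are refilled and they are left out, the rate is biased upward

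*Combined protocol and SAP*

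**What the plan says.** Section 5.9 does not intend chemotherapy to restart after ablation. If the treating physician thinks it is warranted, "then the patient will be considered to have progressed and will be taken off trial and replaced". The example given is that "the patient develops a lesion that is not amenable to ablation". This is the only replacement rule in the documents.

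The primary endpoint is set out in section 2.1: "PFR is defined as the percentage of patients with no progression (local recurrence of an ablated lesion or the appearance of a new lesion", assessed 3 months after ablation. Section 9.4.5 repeats the definition.

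On who is analysed, section 5.6 says "All patients who undergo ablation are evaluable for disease response provided they have had at least one disease assessment". Section 11.2 plans Kaplan-Meier estimates of 3-month PFS for patients given ablation. Section 5.10 adds "After progression, patients will be followed for survival every 3 months".

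On size, section 11.1 sets a null rate of 20% against an alternative of at least 40%. It says "An enrollment of 36 patients can achieve at least 80% power", using a "two-sided test of one-sample proportion at a significance level of 0.05".

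**The concern.** The lesion named in section 5.9 is a new lesion, and a new lesion is progression under sections 2.1 and 9.4.5. When it appears within 3 months, the patient has failed the primary endpoint, and that failure is what triggers replacement.

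In ordinary use, replacing a patient means that another takes the place in the planned number. No section says whether the replaced patient still counts in the PFR denominator, or whether the 36 include such patients. If the place is refilled and the replaced patient is left out, a failure leaves the denominator and someone who may succeed comes in.

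The trial has one arm and tests one proportion against a fixed 20%. There is no control group in which the same selection would occur, so any bias goes straight into the primary result.

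**Working it through.** **Inputs.** From section 11.1: p0 = 0.20, p1 = 0.40, N = 36, two-sided alpha 0.05, one-sample test of a proportion. The share of 3-month progressors who are replaced, f, is not in the documents. I assume 5%, 12.5% and 25%.

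**Step 1. Reproduce the plan's sample size.** With the normal approximation,

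n = [(1.960·√(0.2·0.8) + 0.8416·√(0.4·0.6)) / 0.20]² = 35.78, rounded up to 36.

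Power at 36 is 80.2% and at 35 is 79.2%. The stated figure reproduces, so the sample size is not in question.

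**Step 2. Cut-offs for success with 36 patients.**

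- z-test: 12/36 gives z = (0.3333 − 0.20)/√(0.16/36) = 2.00, and 11/36 gives 1.58. The cut is 12.
- Exact binomial with at most 0.025 in the upper tail: P(X ≥ 12) = 0.042 and P(X ≥ 13) = 0.018 at a true 20%. The cut is 13.

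Section 11.1 does not name the form of the test. The z form matches the stated power, but I carry both.

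**Step 3. Expected rate if places are refilled and the replaced patients left out.** A share f of progressors leaves the analysed set, so the rate among the 36 analysed is

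q = p / [p + (1 − p)(1 − f)].

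The expected number replaced while filling 36 places is 36·(1 − p)f / [1 − (1 − p)f].

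For example, with p = 0.20 and f = 0.125: q = 0.20/(0.20 + 0.80·0.875) = 0.20/0.90 = 0.222, and the number replaced is 36·0.10/0.90 = 4.

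**Step 4. Chance of a false success at a true 20%,** that is, P(X ≥ cut) for a binomial with 36 patients and rate q:

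| f (assumed) | Expected number replaced | Apparent rate | Cut 12/36 (z) | Cut 13/36 (exact) |
|---|---|---|---|---|
| 0 | 0 | 20.0% | 0.042 | 0.018 |
| 5% | 1.5 | 20.8% | 0.056 | 0.025 |
| 12.5% | 4 | 22.2% | 0.084 | 0.041 |
| 25% | 9 | 25.0% | 0.167 | 0.092 |

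**Step 5. The other reading.** If each replaced patient stays in the analysis as a progression, no failure is removed. The expected rate stays at 20% (or 40%) and the bias is zero.

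**The case against.** The strongest reply is that the text already favours retention. Section 5.9 first classes the patient as progressed, which would serve little purpose if the patient were then dropped from the analysis of progression. Section 5.6 makes every ablated patient with one assessment evaluable, and the lesion in the example would ordinarily be found at such an assessment. Section 11.2 analyses ablated patients with no exclusion. Section 5.10 keeps following patients after progression, and being taken off trial may mean no more than leaving protocol follow-up.

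Much of this stands, and it makes zero bias a real possibility. It does not settle the point. Section 5.6 speaks of disease response, and neither it nor section 11.2 mentions replaced patients or the 36. Survival follow-up does not define the PFR denominator. If every replaced patient is also analysed, the analysed number exceeds 36, for which section 11.1 makes no provision.

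It is also fair to say that the size is wholly assumed, since the documents give no replacement frequency.

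Three stronger inferences are tempting but not supported:

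- **That the plan does exclude progressed patients.** No section says so; the text is unresolved.
- **That the bias could equally run downward,** because section 5.9 has no time limit and a restart after 3 months could remove a success. That means erasing a 3-month result already observed, and the documents give this little support.
- **That one replaced patient decides the trial.** With the z-test, 12/36 gives p = 0.046 and 12/37 gives z = 1.89, p = 0.059. This holds only for that form of test at its boundary: the exact two-sided p at 12/36 is already 0.058.

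**Conclusion.** The concern holds in conditional form. Section 5.9 contains an actual rule that ties replacement to the primary-endpoint event, and no section says what happens to the replaced patient in the analysis. If places are refilled and the replaced patients left out, the 3-month PFR is biased upward, by about 1 to 5 percentage points at a true 20% over the assumed range. The false-positive rate rises under either form of test, reaching about four times its nominal value at 12/36 (0.167/0.042) and five times at 13/36 (0.092/0.018) when 25% of progressors are replaced. If they are kept as progressions, nothing changes.

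The missing or unclear treatment of these patients is certain. The size of any bias is not, because it rests on the assumed f and on which reading is applied. The point should be fixed, because the choice could otherwise be made once outcomes are known.

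Sections 2.1 and 9.4.5 do not list death as a failure, while section 11 uses PFS. That mismatch is a separate matter and plays no part here.

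**What to change.** - **Section 5.9:** remove replacement for ablated patients counted as progressed. Limit it to registered patients who were never ablated.
- **Sections 5.6 and 11.2:** state that every ablated patient stays in the primary PFR/PFS analysis, that progression under section 5.9 on or before 3 months is a failure, and that a later restart of chemotherapy leaves the observed 3-month result unchanged.
- **Section 11.1:** state that the 36 are ablated patients.

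These changes do not touch when chemotherapy may resume. No new data are needed to count these patients, because section 5.9 already classes them as progressed.

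With 36 ablated patients all analysed, the planned power of 80.2% by the normal approximation and the z-test upper tail of 0.042 are kept. The costs are a possibly lower reported PFR than under refilling, and a few more registrations if some patients are never ablated. If 5% or 10% of those registered are never ablated (assumed), 36/0.95 = 37.9, so about 38, or 36/0.90 = 40 registrations give 36 ablated patients.

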5.10 Duration of Follow-up

Patients will be followed every 9 weeks for the first year, every 12 weeks for the second year, and then every 6 months for 5 years or until death, progression, consent is withdrawn, or the study is closed, whichever occurs first. Patients will be followed by CT or PET scan and office visits every 9 weeks. CT and PET scans can be performed at outside facilities and mailed to us for review by our radiologists. Patients removed from study for unacceptable adverse events will be followed until resolution or stabilization of the adverse event. After progression, patients will be followed for survival every 3 months.

6.0 REGULATORY AND REPORTING REQUIREMENTS

The entities providing oversight of safety and compliance with the protocol require reporting as outline below.

The Washington University Human Research Protection Office (HRPO) requires that all events meeting the definition of unanticipated problem or serious noncompliance be reported as outlined in Section 6.2.

6.1 Definitions

6.1.1 Adverse Events (AEs)

Definition: any unfavorable medical occurrence in a human subject including any abnormal sign, symptom, or disease.

Grading: the descriptions and grading scales found in the revised NCI Common Terminology Criteria for Adverse Events (CTCAE) version 4.0 will be utilized for all toxicity reporting. A copy of the CTCAE version 4.0 can be downloaded from the CTEP website.

Attribution (relatedness), Expectedness, and Seriousness: the definitions for the terms listed that should be used are those provided by the Department of Health and Human Services' Office for Human Research Protections (OHRP). A copy of this guidance can be found on OHRP's website: <http://www.hhs.gov/ohrp/policy/advevntguid.html>

Only AEs that are related to the ablation procedure should be reported for study data.

6.1.2 Serious Adverse Event (SAE)

Definition: any adverse event related to the ablation procedure that results in any of the following outcomes:

- Death
- A life-threatening adverse drug experience
- Inpatient hospitalization or prolongation of existing hospitalization
- A persistent or significant disability/incapacity (i.e., a substantial disruption of a person's ability to conduct normal life functions)
- A congenital anomaly/birth defect
- Any other experience which, based upon appropriate medical judgment, may jeopardize the subject and may require medical or surgical intervention to prevent one of the outcomes listed above

6.1.3 Unexpected Adverse Experience

Definition: any adverse experience related to the ablation procedure, the specificity or severity of which is not consistent with the current investigator brochure (or risk information, if an IB is not required or available).

6.1.4 Life-Threatening Adverse Experience

Definition: any adverse experience, related to the ablation procedure, that places the subject (in the view of the investigator) at immediate risk of death from the reaction as it occurred, i.e., it does not include a reaction that, had it occurred in a more severe form, might have caused death.

6.1.5 Unanticipated Problems

Definition:

- unexpected (in terms of nature, severity, or frequency) given (a) the research procedures that are described in the protocol-related documents, such as the IRB-approved research protocol and informed consent document; and (b) the characteristics of the subject population being studied;
- related or possibly related to participation in the research (in this guidance document, possibly related means there is a reasonable possibility that the incident, experience, or outcome may have been caused by the procedures involved in the research); and
- suggests that the research places subjects or others at a greater risk of harm (including physical, psychological, economic, or social harm) than was previously known or recognized.

6.1.6 Noncompliance

Definition: failure to follow any applicable regulation or institutional policies that govern human subjects research or failure to follow the determinations of the IRB. Noncompliance may occur due to lack of knowledge or due to deliberate choice to ignore regulations, institutional policies, or determinations of the IRB.

6.1.7 Serious Noncompliance

Definition: noncompliance that materially increases risks, that results in substantial harm to subjects or others, or that materially compromises the rights or welfare of participants.

6.1.8 Protocol Exceptions

Definition: A planned deviation from the approved protocol that are under the research team's control. Exceptions apply only to a single participant or a singular situation.

Pre-approval of all protocol exceptions must be obtained prior to the event.

6.2 Reporting to the Human Research Protection Office (HRPO) at Washington University

The PI is required to promptly notify the IRB of the following events:

- Any unanticipated problems involving risks to participants or others which occur at WU, any BJH or SLCH institution, or that impacts participants or the conduct of the study.
- Noncompliance with federal regulations or the requirements or determinations of the IRB.
- Receipt of new information that may impact the willingness of participants to participate or continue participation in the research study.

These events must be reported to the IRB within **10 working days** of the occurrence of the event or notification to the PI of the event. The death of a research participant that qualifies as a reportable event should be reported within **1 working day** of the occurrence of the event or notification to the PI of the event.

6.3 Reporting to the Quality Assurance and Safety Monitoring Committee (QASMC) at Washington University

The PI is required to notify the QASMC of any unanticipated problem occurring at WU or any BJH or SLCH institution that has been reported to and acknowledged by HRPO as reportable. (Unanticipated problems reported to HRPO and withdrawn during the review process need not be reported to QASMC.)

QASMC must be notified within **10 days** of receipt of IRB acknowledgment via email to a QASMC auditor.

6.4 Timeframe for Reporting Required Events

Reportable adverse events will be tracked for 30 days following ablation. Only AEs that are related to the ablation procedure should be reported for study data.

Deaths	
Any reportable death while on study or within 30 days of study	Immediately, within 24 hours, to PI and the IRB
Any reportable death while off study	Immediately, within 24 hours, to PI and the IRB
Adverse Events/Unanticipated Problems	
Any reportable adverse events as described in Sections 6.1.1 and 6.1.2 (other than death)	Immediately, within 24 hours to PI and within 10 working days to the IRB
All adverse events regardless of grade and attribution should be submitted cumulatively	Include in DSM report
Noncompliance and Serious Noncompliance	
All noncompliance and serious noncompliance as described in Sections 6.1.6 and 6.1.7	Immediately, within 24 hours, to PI and within 10 working days to the IRB

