7.0 STUDY CALENDAR

Baseline evaluations are to be conducted within 3 weeks prior to start of protocol therapy. Scans and x-rays must be done no more than 3 weeks prior to the start of ablation.

	Baseline	Ablation	1 day after ablation	1 month after ablation	Follow-up ^d	Progression
Physical exam, incl. medical history, weight, VS, PS	X					
CBC	X					
CMP	X					
PT/PTT and INR	X					
Pregnancy test ^a	X					
IR evaluation ^b	X					
CT or PET scan					X ^d	
FACT-G7	X		X	X		X
BPI short form	X		X	X		X
Adverse events		X ^c				
Survival follow-up						X ^e

a: Women of childbearing potential only

b: Patients must have 10 or fewer treatable lesions when enrolled in the study and will be seen in consultation by an experienced interventional oncologic radiologist with evaluation of available PET, CT, MR, and US images for eligibility and lesion accessibility

c: Tracked for 30 days following ablation

d: The patients will be imaged as per routine care at the following time points: 6 weeks post first-procedure, every 9 weeks for the first year, every 12 weeks for the second year, and every 6 months for 5 years or until death or radiographic progression, whichever comes first.

e. After progression, patients will be followed every 3 months for survival only.

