8.0 DATA SUBMISSION SCHEDULE

Case report forms with appropriate source documentation will be completed according to the schedule listed in this section.

Case Report Form	Submission Schedule
Original Consent Form	Prior to registration
Registration Form Eligibility Form On-Study Form	Prior to starting treatment
Ablation Form	After treatment
Toxicity Form	30 days following ablation
Tumor Measurement Form Follow Up Form	Baseline 6 weeks after ablation Every 9 weeks during Year 1 Every 12 weeks during Year 2 Every 6 months for all subsequent years for 5 years or until progression or death Every 3 months after progression (survival only)
QOL Form	Baseline 1 day after ablation 1 month after ablation Progression

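### Study data are limited to ablation-related AEs, but the DSM report must list AEs of any attribution, and no source for the unrelated ones is named

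*Combined protocol and SAP*

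**What the plan says.** Section 6.1.1 defines an AE broadly, as "any unfavorable medical occurrence in a human subject including any abnormal sign, symptom, or disease", with no condition on cause. It then narrows what is recorded: "Only AEs that are related to the ablation procedure should be reported for study data". Section 6.4 repeats that sentence.

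Section 6.1.2 makes relatedness part of the definition of a serious AE (SAE): "any adverse event related to the ablation procedure that results in any of the following outcomes".

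The reporting table in Section 6.4 sets a wider scope for the monitoring committee. It says "All adverse events regardless of grade and attribution should be submitted cumulatively", with the instruction "Include in DSM report". Another row of that table sends reportable AEs to the principal investigator and the IRB, and identifies them by cross-reference to Sections 6.1.1 and 6.1.2.

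On timing, Section 6.4 says "Reportable adverse events will be tracked for 30 days following ablation", while the footnote to the AE row of the study calendar (Section 7.0) says "Tracked for 30 days following ablation" without limiting it to reportable events. The one form in Section 8.0 meant for AEs is the "Toxicity Form", due 30 days after ablation.

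Section 10.0 asks for a toxicity summary in each semi-annual DSM report. It has the principal investigator review the data of all patients at least every six months, and has AEs reported to the HRPO and QASMC, under institutional guidelines, once the study team learns of them.

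**The concern.** Two rules in the same section set different scopes for AE information, and the narrower one governs the only named collection form. A coordinator who follows Sections 6.1.1 and 6.4 leaves an event judged unrelated off the Toxicity Form. Whoever prepares the DSM report then needs that event and is not told where to find it.

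The second issue is the order of steps. When attribution is a field on a form, a later reader can tabulate events under any attribution and question the calls. Here it is a condition for entry, so the study data hold only the events that met it. Attribution is a real judgement in this population: patients have metastatic sarcoma, have just stopped 6-12 cycles of chemotherapy, and may have up to 10 lesions ablated by more than one technique. With a single arm, there is no comparator rate against which to judge an all-cause AE rate. The study data as specified would not supply even the all-cause rate itself.

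At stake are the completeness of the DSM report and the safety description of the trial.

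**Working it through.** The plan gives no figure on this point, so there is none to reproduce and no formula applies. The check sets the scope rules side by side.

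| Place | What it governs | Attribution | Window |
|---|---|---|---|
| 6.1.1, definition | What an AE is | Any | None stated |
| 6.1.1 and 6.4, text | AEs in study data | Related only | 30 days, reportable AEs (6.4) |
| 6.1.2 | What an SAE is | Related only | None stated |
| 6.4, IRB row | AEs to investigator and IRB | By reference to 6.1.1 and 6.1.2 | As for reportable AEs |
| 6.4, DSM row | Cumulative list in DSM report | Any | None stated |
| 7.0, AE row | AE tracking | None stated | 30 days |
| 8.0, Toxicity Form | AE data collection | None stated; under the 6.1.1 and 6.4 rule | Due at 30 days |
| 10.0 | DSM report content | None stated | None stated |

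1. Take an AE within 30 days that the team judges unrelated. It is an AE under the definition in 6.1.1. The study-data rule keeps it out of the Toxicity Form. The DSM row requires it in the report. Both rules can be met only if the report draws on something other than the study data.

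2. Is another source named? Section 8.0 lists no second AE form. Section 7.0 has one AE row. Section 10.0 mentions review of patient data but does not say that the AE list is compiled from that review, or how.

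3. Would source records reliably supply the event? The calendar places the physical examination, CBC and CMP at baseline only. Its scheduled contacts after ablation and within about a month are the 1-day and 1-month questionnaires, which Section 5.5 allows by phone. The first post-ablation scan is at about 6 weeks (42 days), and the office visits in Section 5.10 are every 9 weeks, both beyond 30 days. Source records may hold the event, but the plan schedules little that would make sure of it.

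4. Could the DSM row mean all AEs already accepted as related, whatever the degree of relatedness? That would remove the conflict, but the row does not say so, and the AE definition it relies on has no relatedness condition.

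5. Section 6.1.5 counts possibly related events as potential unanticipated problems, while 6.1.1, 6.1.2 and 6.4 say only related. The handling of possibly related AEs in the study data is therefore also unstated.

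6. Is any planned result affected? The objectives in Section 2.0 are 3-month progression-free rate, overall survival, quality of life and pain. Section 11.0 plans no analysis of a toxicity rate. No efficacy estimate, test or sample size depends on this rule.

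**The case against.** The strongest reply is that the two rules govern different outputs. The restriction is on study data; the wide scope is for a report to a monitoring committee. Nothing says that the report must be built from the study database alone. Section 10.0 gives the investigator sight of all patient data every six months and a duty, with no relatedness condition, to report AEs to the QASMC. Unanticipated problems reach the QASMC, once acknowledged by the HRPO, even when only possibly related, and deaths are followed for overall survival whatever their cause.

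Much of this stands. A reader might infer that the DSM summary cannot be produced at all, that unrelated events are never captured anywhere, or that the committee cannot see them. The documents do not support those readings: a report compiled from source records is open to the investigator, and Section 8.0 requires source documentation with the forms. A reader might also want a figure for how far a complication rate would be understated. The documents give neither an expected complication rate nor an accuracy of attribution, so any such figure would only restate what was assumed.

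What the reply does not remove is that the source-record route is nowhere specified, and that it would leave the study data themselves unable to support a check on attribution.

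It can also be said that collecting only related AEs is a deliberate economy. That may be so, but then the DSM row asks for something that the plan chose not to collect, and the text still has to be reconciled.

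**Conclusion.** The point holds as an internal inconsistency in the AE rules. The all-attribution list for the DSM report cannot be built from the study data as specified, and no other form or collection route is named. Because attribution is decided before capture, the study data cannot be used to re-examine it or to give an all-cause AE rate.

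Its size is limited. It touches DSM reporting and the description of safety in about 36 patients, and leaves the efficacy conclusions alone. How many events would be left out cannot be derived from the documents. The conclusion assumes that staff follow the study-data rule as written and that the Toxicity Form is subject to it. It does not go as far as saying that the committee would be uninformed, since Section 10.0 leaves another route open. The text should be corrected because the change is cheap and improves safety monitoring.

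**What to change.** - **Sections 6.1.1 and 6.4:** replace the related-only sentence with a rule that every AE in the existing 30-day window is recorded on the Toxicity Form, with grade, seriousness and attribution as separate fields. Say how possibly related events are coded.
- **Section 6.1.2:** define an SAE by outcome only.
- **Section 6.4, IRB row:** this row takes its scope from Sections 6.1.1 and 6.1.2, so write the relatedness condition into the row itself. Without this edit, the changes above would widen expedited reporting; with it, expedited reporting is unchanged.
- **Section 6.4, DSM row:** state the window for the cumulative list and that it is tabulated from all recorded AEs, with a separate table of ablation-related events. When stating the window, say which procedure starts it, since Section 5.6 counts from the first procedure and Section 6.4 only from ablation.
- **Sections 8.0 and 10.0:** align the Toxicity Form entry and the DSM toxicity summary with these rules, and name the source of the DSM list.

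Aligning the DSM row with the related-only rule, or naming source records as its source, would also end the contradiction on paper. Neither would let attribution be re-examined from the study data.

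The cost is a protocol wording amendment, an attribution field if the form lacks one, and a little more data entry over 30 days for about 36 patients.
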